### **4.0 Participants and Recruitment**

*Participants will be 64 Black/African American men ages 55 years or older and meet the inclusion criteria listed below. During the Phase II pilot we will individually randomize each participant with a 50/50 randomization scheme to either the peer led DSMS or a control group. Four of the participants will attend 30- hours of training and function as peer leaders during the intervention DSMES.*

**Inclusion:** Inclusion criteria for the Phase II (intervention) will include males age 55 or older who are Black/African American, and who've had diagnosis of T2D for a six-month duration or longer.

**Exclusion:** Exclusion criteria for Phase II will include: non-ambulatory, serious health conditions (morbid obesity and severe symptomatic heart disease, visual impairment, renal failure, and peripheral neuropathy), psychiatric illness (severity requiring hospitalization) or cognitive deficit (illness determined using the Montreal Cognitive Assessment tool) and serious diabetes complications (e.g. blindness) that would impede meaningful participation. We considered restricting eligibility to a higher-risk population of participants with  $A1c \geq 8\%$ . Preliminary data suggest that over 50% of the proposed study sample will have an  $A1c \geq 8\%$ . Focusing on all older Black men with T2D allows us to cast a wide net for secondary prevention and public health impact. Persons who meet eligibility criteria will be invited to participate in the baseline screening assessment. While we have chosen the above eligibility criteria based on previous work, we will make adjustments to the future, larger trial, based on results and feedback from our proposed pilot.

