**Baseline Assessment** (Assessment Battery) All individuals that meet initial phone screening criteria and agree to participate will complete a baseline assessment. The physiological testing portion of the baseline assessment will be held in person at either St. Patrick Senior Center or Ypsilanti Seventh Day Adventist Church and the self-report questionnaire will be completed by the participant virtually or over the phone with a study team member. During the assessment the participant will be asked to complete questionnaires and interviews to determine if the participant is eligible to participate based on inclusion and exclusion criteria. Baseline assessments will last about two hours total. The PI will train all research staff in standardized data collection. Trained research staff will take biometric data of participants including height, weight, blood pressure, and A1c. Participant A1c values will be analyzed on site using a DCA Vantage Analyzer. All participants, including peer leader participants, will be paid \$20 for completing the assessment and the same assessments at T0 (baseline) and T1 (post-treatment).

**Randomization** Participants will be randomized to the peer leader diabetes self-management support (DSMS) group or a control group using a 50/50 randomization scheme. Participants will be aware if they are in the intervention group or the control group.

**Intervention (Peer Leader DSMS n=30)** Participants randomized to the peer led DSMS group will receive 6 100-minute weekly sessions of diabetes self-management education (DSME) delivered by a certified diabetes care and education specialists (CDCES) and co-facilitated by a peer leader (PL) delivered via the Zoom for Health a U-M service may be used for Protected Health Information (PHI, regulated by HIPPA). Next, participants will transition into 6 90-minute weekly PL led DSMS sessions

intentionally designed for older Black men with T2D. The CDCES will provide oversight to the PL and be available by phone if any clinical questions arise during the session.

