### **Secondary Outcome Measures**

Adherence to gender norms will be measured using the Male Role Norms Inventory-Short Form. BMI will be calculated using height and weight. Height will be measured using a stadiometer. Weight will be measured on a high quality, calibrated digital scale. BP will be measured using a digital sphygmomanometer.

Diabetes Social Support will be measured using the Diabetes Social Support Questionnaire. Diabetes-related Distress will be measured using Diabetes Distress Scale (SF-12) and lastly, a validated Diabetes Quality of Life will be used to measure quality of life. Participants will also complete questionnaires that assess socio-demographic, behavioral, psychosocial, and health services utilization and are validated in diverse populations with diabetes.

**Specific Aim 1:** Qualitative analyses will be conducted during the development phase and on the post-intervention focus groups and interviews. First, we will develop codes utilizing a grounded theory approach and will start with the formulation of categories and definitions developed directly from the text. Content from transcripts will be coded for themes and patterns. Through this process a coding manual and definitions will be finalized. The refined manual will be used to guide ongoing coding and pairs of coders will read subsequent transcripts keeping codes that achieve 80% agreement on code application. Analyses will be conducted using Dedoose. This data will be used to conduct a final refinement of treatment content as needed.

**Specific Aim 2:** The proposed study includes a sample size of 64 Black men, 30 in the intervention arm, 30 in the control arm and 4 trained as peer leaders for the intervention arm. We will assess the impact of the intervention on diabetes management and HbA1c (primary outcomes) and on secondary outcomes using multilevel modeling, with intervention group as a between-subjects factor (2 levels) and time as a within subjects factor (3 levels). HbA1c, diabetes self-management, and social support at baseline, 3 and 6 months will be used as the dependent variables. Independent variables include intervention group, time of assessment, and interaction between time and intervention

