group. Random effects will be allowed for the intercept (to allow differences in baseline measurements) and the slope (to allow differences in the trajectories of change). Covariates e.g. length of time since diabetes diagnosis, age will be tested as predictors of the outcome and retained if significant at  $p < .10$ .

**Power Analysis:** Assuming 20% attrition, we expect a final sample size of 48, approximately 12 per group (with 2 groups in the treatment arm). If we assume correlations of 0.25 between successive measurements of HbA1c, then this sample size will yield power of 0.8 to detect a difference of 0.6 standard deviation between average values of HbA1c in treatment and control groups.

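### The arm-by-time contrast does not condition on the baseline outcome, so the effect estimate is less precise than the collected data allow and keeps most of any chance baseline gap

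*Combined protocol and SAP*

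**What the plan says.** The outcome model is in Section 7.0, Specific Aim 2. Baseline is one of the outcome occasions: "HbA1c, diabetes self-management, and social support at baseline, 3 and 6 months will be used as the dependent variables". The fixed effects are arm, time and their interaction. Each man also has a random intercept and slope: "Random effects will be allowed for the intercept (to allow differences in baseline measurements". Diabetes duration and age are given as examples of covariates, kept only if they reach p < .10. Neither a baseline covariate nor a constraint of equal arm means at baseline is stated.

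The Power Analysis paragraph supplies the only correlation: "If we assume correlations of 0.25 between successive measurements of HbA1c". It claims power of 0.8 for a 0.6 SD difference with 48 men analysed.

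Section 4.0 describes the allocation: "we will individually randomize each participant with a 50/50 randomization scheme". Section 5.0, Randomization, repeats the ratio and gives no list method.

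The visit schedule is not consistent. Section 1.0 and Section 5.0 (Baseline Assessment and Follow-Ups) describe baseline and three months only. Section 2.0 adds a further 3-month follow-up, and Section 7.0 gives time three levels.

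**The concern.** The parenthesis about baseline differences can be read as saying that the random intercept deals with unequal starting points. It does so for men, not for arms. Because the arm main effect is free, the model fits whatever baseline difference chance produces and then measures change from it. When the correlation between visits is below 1, part of a chance gap is expected to close by follow-up with no intervention effect, and the interaction term counts that closing as effect.

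Sections 1.0 and 3.0 make effect-size estimation a purpose of the pilot, with a larger trial to follow. The single realised estimate is what will be carried forward, so its precision matters, and so does its dependence on a baseline gap that anyone can see.

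**Working it through.** **Inputs.** Analysed number: 60 × 0.8 = 48, taken as 24 per arm. Correlation r = 0.25 and target 0.6 SD, both from the Power Analysis paragraph. Alpha and sidedness are not stated, so two-sided 0.05 is assumed. Equal variance at each visit is assumed, in SD units. The values r = 0.5 and 0.7 are assumptions, used to show the range. Clustering by session group is left out.

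**The plan's own figure.** Power = Φ(0.6/√(2v/24) − 1.96), where v is the variance of the per-man summary and all visits correlate at 0.25.

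| Contrast | v | Power |
|---|---|---|
| Mean of two follow-ups, baseline-adjusted | (1+r)/2 − r² = 0.5625 | 0.791 |
| Mean of all three visits | (1+2r)/3 = 0.50 | 0.836 |
| Mean of two follow-ups minus baseline | (1+r)/2 + 1 − 2r = 1.125 | 0.500 |
| One follow-up minus baseline | 2(1−r) = 1.5 | 0.396 |
| One follow-up, baseline-adjusted | 1 − r² = 0.9375 | 0.574 |

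Of these, the baseline-adjusted mean of two follow-ups comes closest to the stated 0.8. Neither change contrast reaches it, even one-sided (0.624 and 0.521).

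**What the model estimates.** With complete data at two visits and a free arm effect, the interaction is (change in intervention mean) − (change in control mean). Mixed-model fits with a random intercept, and with intercept plus slope, matched this to at least 12 decimals.

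**Error given a baseline gap D** (intervention minus control, in SD). With no intervention effect, the expected gap at follow-up is rD, so the expected contrast is rD − D = −(1−r)D. That is 75% of D at r = 0.25, 50% at 0.5 and 30% at 0.7. In 40,000 simulated trials at r = 0.25 the carry-over per unit of D was −0.745 for the change contrast and 0.006 after adjustment. The mean error over all trials was 0.001 SD.

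**Precision at 24 per arm.** Half-width = 1.96√(2v/24).

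| r | v, change | v, adjusted | Variance cut | Half-width, SD |
|---|---|---|---|---|
| 0.25 | 1.50 | 0.9375 | 37.5% | 0.69 to 0.55 |
| 0.5 | 1.00 | 0.75 | 25% | 0.57 to 0.49 |
| 0.7 | 0.60 | 0.51 | 15% | 0.44 to 0.40 |

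**One cost, not two.** 2(1−r) − (1−r²) = (1−r)². At r = 0.25 this is 1.5 − 0.9375 = 0.5625 = 0.75². The variance removed by adjustment is exactly the variance of the carried-over gap.

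**Typical gap.** The SD of D is √(2/24) = 0.289, so the median of |D| is 0.6745 × 0.289 = 0.195, and 0.75 × 0.195 = 0.146 SD. If a likelihood fit keeps the baseline rows of men who drop out, the gap is between 30 and 30: 0.6745 × √(2/30) = 0.174, and 0.75 × 0.174 = 0.131 SD. At r = 0.7 the shift at 24 per arm is 0.3 × 0.195 = 0.06 SD.

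**Same allowance for precision.** With those rows kept and ignorable dropout, the per-arm variance of the change contrast at r = 0.25 is 0.9375/24 + 0.5625/30 = 0.0578, against 1.5/24 = 0.0625. The half-width is then 1.96√(2 × 0.0578) = 0.67. The saving from adjustment is 0.01875/0.0578 = 32%, instead of 37.5%.

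**The case against.** The strongest reply is that randomization already makes the change contrast valid. That stands: averaged over allocations it is unbiased, and its 0.69 SD half-width already contains the chance imbalance. A reader might infer that the planned estimate is biased, or that the 0.15 SD shift adds to the variance loss. Neither follows.

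Nor does a typical gap inflate the error rate. At the median gap with r = 0.25, the conditional two-sided type I error is about 0.027, and at D = 0.3 it is 0.048. It rises to 0.128 at D = 0.5, a gap exceeded in about 8% of allocations.

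A reader might also blame the open HbA1c entry in Section 4.0. Entry without an HbA1c limit does not produce the carry-over; chance imbalance and r below 1 do. The document gives its reason for the choice: "Focusing on all older Black men with T2D allows us to cast a wide net for secondary prevention and public health impact". It expects more than half of the men at 8% or above, without saying how many more.

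A third inference is that randomization disregards baseline HbA1c. The documents are silent on how the list is built, so one can say only that no stratification is described. Once the model conditions on baseline, no further gain from stratifying has been shown.

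The open covariate list does not answer the point. Baseline HbA1c is already an outcome row, so it could not also serve as a covariate without changing the model, and it would face the p < .10 screen.

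Finally, the size depends on r, for which 0.25 is given without a basis. That is correct, and the range above is the answer to it.

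**Conclusion.** The point holds as a loss of precision, with an error that depends on the baseline gap that happens to occur. At the plan's r = 0.25 with 24 analysed per arm, conditioning on baseline removes 37.5% of the contrast variance (about 32% if dropouts' baseline rows are retained). Power for 0.6 SD with one follow-up rises from 0.40 to 0.57. If r is nearer 0.7 the saving is 15% and the carry-over 30% of the gap: still a gain, but a modest one.

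The result assumes equal variances across visits, two-sided 0.05 for the power figures, and no clustering. It does not make the pilot's estimate precise: 0.55 SD remains wide beside a 0.6 SD target. The correlation applies to HbA1c only. None is given for the self-management scale, which Sections 1.0 and 2.0 name as the primary outcome (Section 7.0 lists both as primary), so the gain there cannot be sized, although the same algebra applies.

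**What to change.** In Section 7.0, Specific Aim 2, define the effect as the difference between arms at follow-up, conditional on the baseline value of the same outcome. Either of two forms will do:

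- follow-up values as the outcome, with baseline as a prespecified fixed covariate that is always kept and not put through the p < .10 screen; or
- baseline kept as an outcome row, with the arm means constrained to be equal at baseline.

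Apply the chosen form to every outcome. Reconcile the baseline-and-three-months schedule in Sections 1.0 and 5.0 with the three time levels in Section 7.0, then restate the power for the contrast actually planned.

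The cost is one change to the model specification and a revised power sentence. Baseline values are already collected, so no visit, test or staff time is added. Stratifying the allocation by HbA1c is optional and not needed for this gain.

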### **3.0 Aims**

**Aim 1 (Phase 1): Refine existing intervention components from a previous peer leader trial to allow it to be best tailored to the needs of older Black men with T2D by:**

- Conducting 10 interviews with older Black/African American men with T2D.

**Aim 2: Conduct a pilot randomized controlled trial for older Black men with T2D based on what we learn from Aim 1. Development, adaptation, and refinement will involve:**

- Developing a peer led diabetes self-management education and support intervention based on our interviews and previous research.
- Conduct an open pilot study to determine feasibility and acceptability of the peer led diabetes self-management support and estimate intervention effect size on our primary outcome of diabetes self-management behaviors and changes in A1C, as well as on secondary outcomes of change in weight, blood pressure, quality of life, diabetes related-distress, diabetes social support, and adherence to gender norms. Data from the pilot trial will help refine recruitment strategies, training materials, and protocol to be used in a larger clinical study.

**Aim 3: Conduct a qualitative process evaluation of the implementation of peer led DSMS to determine feasibility and acceptability of the intervention by:**

- Recruiting 10-12 stakeholders (facilitators, participants, peer leaders, and certified diabetes care and education specialists) and complete post intervention interviews to identify barriers, perceptions and beliefs surrounding peer led DSMS targeting older Black male populations.

**Overall impact:** Data from the pilot RCT will help refine recruitment strategies, training materials, and the study protocol to be used in a larger cluster RCT. Our study will also identify strategies to increase patient participation in intervention research and improve drop out rates. This goal is in line with the mission of NIDDK to disseminate science-based information on diabetes, to improve people's health and quality of life.

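### Covariates come from an open list and are kept only if p < .10 in the trial's own outcome data; the effect on the average between-arm contrast is small, and fixing the two named covariates in advance removes it

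*Combined protocol and SAP*

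**What the plan says.** The outcome model is set out in section 7.0 under Specific Aim 2. Its terms are: "Independent variables include intervention group, time of assessment, and interaction between time and intervention" group, with random intercept and slope and "time as a within subjects factor (3 levels"). The covariate rule follows: "Covariates e.g. length of time since diabetes diagnosis, age will be tested as predictors of the outcome and retained if significant at" p < .10. The two variables are given as examples. No other section closes the list, says whether arm is in the model used for the screen, or describes a correction, resampling step or sensitivity analysis for the selection.

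The Power Analysis paragraph claims "power of 0.8 to detect a difference of 0.6 standard deviation between average values of HbA1c in treatment and control groups". That contrast is a difference between arm averages, with no covariate term. Under Secondary Outcome Measures, the plan also says: "Participants will also complete questionnaires that assess socio-demographic, behavioral, psychosocial, and health services utilization". It does not call these questionnaires covariates, but nothing in the rule excludes them.

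**The concern.** Choosing covariates by their p-value against the trial outcome, and then reporting the final model as if it had been fixed beforehand, makes the usual standard errors slightly wrong. The direction depends on a detail the plan leaves out.

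- **Arm in the screening model.** Covariates that happen to reduce the residual variance are favoured, so intervals come out slightly too short and type I error slightly too high.
- **Arm left out.** A covariate that is imbalanced by chance can pass the screen because it picks up part of the treatment effect. Adjusting for it then pulls a true effect slightly toward zero.

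Both effects grow with the number of candidates, which the plan leaves open. What is at stake is modest: small errors in the average contrast, and an adjustment set that can be settled after the data are seen and can differ between outcomes.

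**Working it through.** **Inputs from the plan (section 7.0)**
- Allocation: "30 in the intervention arm, 30 in the control arm and 4 trained as peer leaders for the intervention arm".
- Attrition: "Assuming 20% attrition, we expect a final sample size of 48, approximately 12 per group (with 2 groups in the treatment arm"). 60 × 0.8 = 48, taken as 24 per arm.
- Correlation between successive HbA1c values 0.25; three time points; target difference 0.6 SD; power 0.8.

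**Assumed, because the plan does not state them**
- Two-sided alpha 0.05, and equal correlation between all visits.
- Candidates independent and normal. The two named covariates are either unrelated to the outcome or each correlated 0.3 with it; further candidates are noise.
- Six candidates means the two named plus one per questionnaire domain.

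**Step 1. Reproduce the plan's figure and fix the scale.** The variance of a person's average over three visits is (1 + 2 × 0.25)/3 = 0.5 single-measurement SD². The planned 0.6 SD is therefore 0.6/√0.5 = 0.85 SDs of the person's average. With 24 per arm, noncentral t power is 0.82, and 23 per arm is enough for 0.80, so the plan's 48 is essentially reproduced. Reading 0.6 as SDs of the average would give power of only 0.53, so the plan's 0.6 must be on the single-measurement scale.

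**Step 2. Simulate the rule for the average contrast.** Least squares on one average per person, n = 48. Each candidate is tested singly, kept at p < .10, and the model refitted; 60,000 runs per cell. The Monte Carlo SE of a 5% error rate is √(0.05 × 0.95/60,000) = 0.09 points. Each pair is unrelated / correlated 0.3.

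| Rule | Type I error, 2 candidates | Type I error, 6 candidates |
|---|---|---|
| p < .10, arm in screen | 5.3% / 5.5% | 5.7% / 6.2% |
| p < .10, arm left out | 4.9% / 4.9% | 4.7% / 5.1% |
| Two named covariates fixed | 5.0% / 4.9% | 4.8% / 5.0% |

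With arm in the screen, coverage of the 95% interval is 94.6% / 94.5% (two) and 93.9% / 93.9% (six). With the two fixed it is 94.9–95.1%. Repeat runs (20,000 per setting, each named covariate explaining 0–10% of the variance, arm in the screen) gave type I error of 5.3–5.8% for two candidates, 5.8–6.3% for five and 6.5–7.3% for ten.

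**Step 3. Attenuation when arm is left out of the screen.** At a true effect of 0.85 SDs of the person's average:
- Two candidates: about 0.013 / 0.021, or 0.013/0.85 = 1.5% to 0.021/0.85 = 2.5% of the effect.
- Six candidates: about 0.030 / 0.038, or 3.5% to 4.5% of the effect.

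Multiplying by √0.5 gives 0.009 / 0.015 and 0.021 / 0.027 in single-measurement SDs. The sampling SD of the contrast is 0.27–0.29 in SDs of the average (unadjusted, √(2/24) = 0.289). With arm in the screen, or with the two covariates fixed, there is no attenuation.

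**Step 4. The group-by-time term.** A baseline covariate entered as a main effect contributes the same amount at every visit, so it cancels from a within-person change. With complete data the shift is exactly zero. With 20% random dropout, 30 per arm, random intercept and slope (variances 0.25 for intercept, 0.75 for residual and, assumed, 0.05 for slope), the mean absolute shift is 0.002–0.003 single-measurement SD with two candidates and 0.006–0.008 with six. The standard error is 0.33–0.36.

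**Step 5. Price of fixing the two covariates.** If they explain nothing, the variance inflation is 1 + 2/43, and √(1 + 2/43) = 1.023. Simulated mean half-widths are 0.578 unadjusted, 0.575 under the rule with arm in the screen, and 0.592 with both fixed. Fixing is thus 2.4% wider than unadjusted and 2.9% wider than the rule. If each correlates 0.3, the joint R² is 2 × 0.3² = 0.18, and the half-widths are 0.578, 0.534 and 0.536: 7% narrower than unadjusted and 0.3% wider than the rule.

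**The case against.** The strongest objection concerns which quantity is affected. A reader might infer that the rule distorts the effect sizes the pilot is meant to deliver, since Aim 2 sets out to "estimate intervention effect size on our primary outcome of diabetes self-management behaviors and changes in A1C". The documents do not support that. In the specified model an effect on change is the group-by-time term, which Step 4 shows is essentially untouched. The distorted quantity is the average between-arm difference, which appears in the power statement and is not otherwise named as an analysis. This objection stands, and it limits the point.

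Three further objections hold in part:
- Type I inflation needs arm in the screening model, which the plan does not say. Without arm the inflation disappears, but attenuation takes its place, so neither reading is free of cost.
- The six-candidate figures rest on an assumed count; the plan names two variables. It also sets no ceiling, so two is not a limit.
- That the reported p-values and intervals ignore the selection is inferred from silence. The plan describes no allowance; it does not say there will be none.

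Finally, fixing covariates that turn out uninformative costs a little precision. That is true, and Step 5 gives the amount.

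**Conclusion.** The point holds as a minor one. The plan selects from an open covariate list using the trial's own outcome data, and describes no allowance for doing so. For the two named covariates the consequence is under one percentage point of type I error, or an attenuation of at most about 2.5% of the planned effect, on the average contrast only. It grows with the number of candidates, which the plan leaves open.

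The sizes rest on 24 per arm, two-sided 5%, independent normal candidates and the assumed covariate–outcome correlations. Expressing the planned effect as 0.85 SDs of the average also needs the three visits in section 7.0 and equal correlation of 0.25. That the list is open and selected on outcome data needs no assumption. None of this shows that the pilot's estimates of change in HbA1c would be materially biased.

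**What to change.** In section 7.0, Specific Aim 2, replace the p < .10 rule with: *All outcome models include age and years since T2D diagnosis, fixed in advance and kept regardless of significance; any other covariate adjustment is a labelled sensitivity analysis.*

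This closes the list as well as removing the screen; both are needed to restore nominal error. It takes one sentence and uses only variables the plan already names, with no added visit. At worst, if neither covariate predicts the outcome, power for the planned 0.6 SD falls from 0.82 unadjusted to about 0.80. At a joint R² of about 0.05 the loss against no adjustment is recovered (0.82), and at 0.10 power is 0.84.
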